### **4.3 Justification for Dose**

#### **4.3.1 Rationale for Dosing Duration**

Three doses of MK-4482 (administered every 12 hours) were sufficient to demonstrate efficacy in a ferret model of influenza. However, the duration of dosing of MK-4482 required to achieve efficacy against SARS-CoV-2 in humans is unknown. The planned treatment regimen of 5 days in this study is consistent with other acute antiviral treatments such as oseltamivir for influenza and is supported by nonclinical and clinical safety data for MK-4482.

In a 28-day toxicity study of MK-4482 at 17 mg/kg/day (2.2-fold the predicted NHC exposure of 13.27  $\mu$ M\*hr at a dose of 200 mg BID) administered in dogs, reversible hematology changes consistent with bone marrow toxicity became apparent at Day 7 with increasing severity from Day 14 onward. Dosing of MK-4482 up to 800 mg Q12H for 5.5 days has been generally well tolerated by healthy participants in a Phase 1 clinical study; on review of preliminary blinded safety data, no clinically meaningful trends have been observed for changes in clinical laboratory values, vital signs, or ECGs as a function of dose or treatment. Specifically, there have been no clinically significant abnormalities observed in the hematological laboratory tests. Overall, preclinical and Phase 1 clinical observations to date support a ~5-day dosing duration for MK-4482.

#### **4.3.2 Dose Range for Part 1 (Phase 2)**

The dose range planned for Part 1 was derived based on the anticipated clinically efficacious dose range predicted from nonclinical animal models. MK-4482 demonstrated efficacy in ferrets (a relevant species for virus challenge models) against H1N1 at 7 mg/kg BID (in vitro data demonstrated similar MK-4482 potency against H1N1 and SARS-CoV-2). The efficacious 7 mg/kg BID dose in ferrets scales to ~100 mg BID in humans, based on body surface area (assuming a 70 kg adult). This is a common scaling approach used for nucleosides, with some variability in the scaling of the prodrug to active triphosphate conversion from animals to humans.

Part 1 of the study includes evaluation of the 200 mg BID dose, as it is within the efficacious dose range predicted from animals, and includes higher doses in order to characterize the dose- and exposure-response relationship for MK-4482. The highest dose of 800 mg BID has a predicted steady-state mean plasma AUC0-12 exposure of ~32  $\mu\text{M}^*\text{hr}$ , which is 2.4-fold below the mean plasma AUC0-12 exposure at the highest single dose evaluated in adults of 1600 mg.

#### **4.3.3 Dose Selection for Part 2 (Phase 3)**

The Phase 3 dose will be selected based on evaluation of Phase 2 data and will not exceed a dose of 800 mg Q12H. Interim analyses will be conducted as outlined in Section 9.7 to support dose selection.

### **4.4 Beginning and End of Study Definition**

The overall study begins when the first participant (or their legally acceptable representative) provides documented informed consent. The overall study ends when the last participant completes the last study-related contact, withdraws consent, or is lost to follow-up (ie, the participant is unable to be contacted by the investigator).

#### **4.4.1 Clinical Criteria for Early Study Termination**

The clinical study may be terminated early if the extent (incidence and/or severity) of emerging effects/clinical endpoints is such that the risk/benefit ratio to the study population as a whole is unacceptable. In addition, further recruitment in the study or at (a) particular study site(s) may be stopped due to insufficient compliance with the protocol, GCP, and/or other applicable regulatory requirements, procedure-related problems or the number of discontinuations for administrative reasons is too high. Early study termination may also be considered after review of accumulating efficacy and safety data by the eDMC (Section 9.7).

## **5 STUDY POPULATION**

Male/female hospitalized participants  $\geq 18$  years of age with COVID-19 will be enrolled in this study.

Prospective approval of protocol deviations to recruitment and enrollment criteria, also known as protocol waivers or exemptions, is not permitted.

## 5.1 Inclusion Criteria

A participant will be eligible for inclusion in the study if the participant:

### Type of Participant and Disease Characteristics

1. Has documentation of PCR-confirmed SARS-CoV-2 infection with sample collection  $\leq 10$  days prior to the day of randomization.

*Note: PCR is the preferred method; however, with evolving approaches to laboratory confirmation of SARS-CoV-2 infection, other molecular or antigen tests that detect viral RNA or protein are allowed if authorized for use in the country. Serological tests that detect host antibodies generated in response to recent or prior infection are not allowed.*

2. Had initial onset of signs/symptoms attributable to COVID-19 for  $\leq 10$  days prior to the day of randomization and  $\geq 1$  sign/symptom attributable to COVID-19 present at randomization.
3. Requires medical care in the hospital for ongoing clinical manifestations of COVID-19 (not just for public health or quarantine purposes).
4. Has mild, moderate, or severe COVID-19 (Appendix 9).
5. Is willing and able to take oral medication.

### Demographics

6. Is male or female,  $\geq 18$  years of age, at the time of providing informed consent.

### Male Participants

7. Male participants are eligible to participate if they agree to the following during the intervention period and for at least 90 days after the last dose of study intervention:

- Refrain from donating sperm

PLUS either:

- Be abstinent from heterosexual intercourse as their preferred and usual lifestyle (abstinent on a long term and persistent basis) and agree to remain abstinent

OR

- Must agree to use contraception unless confirmed to be azoospermic (vasectomized or secondary to medical cause [Appendix 5]) as detailed below:
- Agree to use a male condom plus partner use of an additional contraceptive method when having penile-vaginal intercourse with a WOCBP who is not currently pregnant. Note: Men with a pregnant or breastfeeding partner must agree to remain abstinent from penile-vaginal intercourse or use a male condom during each episode of penile-vaginal penetration.
- Contraceptive use by men should be consistent with local regulations regarding the methods of contraception for those participating in clinical studies.

## Female Participants

8. A female participant is eligible to participate if she is not pregnant or breastfeeding, and at least one of the following conditions applies:

- Is not a WOCBP

OR

- Is a WOCBP and using a contraceptive method that is highly effective (a low user dependency method OR a user dependent method in combination with barrier method), or be abstinent from heterosexual intercourse as their preferred and usual lifestyle (abstinent on a long-term and persistent basis), as described in Appendix 5 for 28 days from the start of study intervention. The investigator should evaluate the potential for contraceptive method failure (ie, noncompliance, recently initiated) in relationship to the first dose of study intervention.
- A WOCBP must have a negative highly sensitive pregnancy test (serum test is required) within 24 hours before the first dose of study intervention.
- Additional requirements for pregnancy testing during and after study intervention are located in Section 8.3.5.
- The investigator is responsible for review of medical history, menstrual history, and recent sexual activity to decrease the risk for inclusion of a woman with an early undetected pregnancy.
- Contraceptive use by women should be consistent with local regulations regarding the methods of contraception for those participating in clinical studies.
- Given the elevated risk of venous thrombotic events in patients hospitalized with COVID-19 [Benson, L. S., et al 2020] [Spratt, D. I. 2020], estrogen-containing contraceptives must not be started to fulfill the contraceptive requirement of this study at any time during participant's hospitalization. If contraceptives are interrupted as standard of care management of COVID-19 patients and resumed at a later time point, such as at hospital discharge, then abstinence must be practiced for the defined

period of back-up contraception per the contraceptive product labeling. After this period, contraceptive use must adhere to Appendix 5.

## **Informed Consent**

9. Participant (or legally acceptable representative) has provided documented informed consent for the study.

### **5.2 Exclusion Criteria**

The participant must be excluded from the study if the participant:

#### **Medical Conditions**

1. Has critical COVID-19 (Appendix 9) with any of the following:
  - Respiratory failure defined based on resource utilization requiring at least one of the following:
    - Endotracheal intubation and mechanical ventilation, oxygen delivered by high-flow nasal cannula (heated, humidified, oxygen delivered via reinforced nasal cannula at flow rates >20 L/min with fraction of delivered oxygen  $\geq 0.5$ ), noninvasive positive pressure ventilation, ECMO, or clinical diagnosis of respiratory failure (i.e., clinical need for one of the preceding therapies, but preceding therapies not able to be administered in setting of resource limitation)
  - Shock (defined by systolic blood pressure <90 mm Hg, or diastolic blood pressure <60 mm Hg or requiring vasopressors)
  - Multi-organ dysfunction/failure
2. Is on dialysis or has reduced eGFR  $<30 \text{ mL/min}/1.73\text{m}^2$  by the MDRD equation (Appendix 10).
3. Has any of the following conditions:
  - HIV with a recent viral load  $>50 \text{ copies/mL}$  or CD4  $<200 \text{ cell/mm}^3$
  - Chemotherapy required within 6 weeks before randomization
  - A neutrophilic granulocyte absolute count  $<500/\text{mm}^3$
  - Autologous or allogeneic hematopoietic stem cell transplant recipient

4. Has a history of HBV or HCV infection with any of the following:
  - Cirrhosis
  - End-stage liver disease
  - Hepatocellular carcinoma
  - AST and/or ALT > 3X upper limit of normal at screening
5. Has a platelet count <100,000/ $\mu$ L or received a platelet transfusion in the 5 days prior to randomization.
6. Has a history of acute pancreatitis within 3 months prior to randomization or a history of chronic pancreatitis.
7. Has a baseline heart rate of < 50 beats per minute at rest.
8. Has hypersensitivity or other contraindication to any of the components of the study interventions as determined by the investigator.
9. Has any condition for which, in the opinion of the investigator, participation would not be in the best interest of the participant or that could prevent, limit, or confound the protocol-specified assessments including but not limited to:
  - Participants who are not expected to survive longer than 48 hours after randomization, or
  - Participants who are expected to require mechanical ventilation within 48 hours after randomization, or
  - Participants with a recent history of mechanical ventilation, or
  - Participants with conditions that could limit gastrointestinal absorption of capsule contents.

### **Prior/Concomitant Therapy**

10. Is taking or is anticipated to require any prohibited therapies as outlined in Section 6.5.

### **Prior/Concurrent Clinical Study Experience**

11. Is unwilling to abstain from participating in another interventional clinical trial through Day 29 with an investigational compound or device, including those for COVID-19 therapeutics.

### **Diagnostic Assessments**

Not applicable

## Other Exclusions

12. Is anticipated to require transfer to a non-study hospital within 72 hours.
13. Is or has an immediate family member (eg, spouse, parent/legal guardian, sibling, or child) who is investigational site or Sponsor staff directly involved with this study.

## 5.3 Lifestyle Considerations

There are no lifestyle restrictions.

## 5.4 Screen Failures

Screen failures are defined as participants who consent to participate in the clinical study, but are not subsequently randomized in the study. A minimal set of screen failure information is required to ensure transparent reporting of screen failure participants to meet the CONSORT publishing requirements and to respond to queries from regulatory authorities. Minimal information includes demography, screen failure details, eligibility criteria, and any AEs or SAEs meeting reporting requirements as outlined in the data entry guidelines.

## 5.5 Participant Replacement Strategy

A participant who discontinues from study intervention OR withdraws from the study will not be replaced.

# 6 STUDY INTERVENTION

Study intervention is defined as any investigational intervention(s), marketed product(s), placebo, or medical device(s) intended to be administered to a study participant according to the study protocol.

Clinical supplies (study intervention[s] provided by the Sponsor) will be packaged to support enrollment. Clinical supplies will be affixed with a clinical label in accordance with regulatory requirements.

## 6.1 Study Intervention(s) Administered

The study intervention(s) to be used in this study are outlined in [Table 1](#).

Table 1 Study Interventions

Arm Name	Arm Type	Intervention Name	Intervention Type	Dose Formulation a	Unit Dose Strength(s)	Dosage Level(s) b	Route of Administration	Regimen/Treatment Period	Use	IMP/NIMP	Sourcing
MK-4482	Experimental	MK-4482	Drug	Capsule	200 mg	Part 1: 200 mg, 400 mg, 800 mg Part 2: Dose to be selected	Oral	Q12H 5 days (10 doses total)	Experimental	IMP	Central
Placebo	Placebo Comparator	Placebo Matching MK-4482	Drug	Capsule	0 mg	Part 1: N/A Part 2: N/A	Oral	Q12H 5 days (10 doses total)	Placebo	IMP	Central

N/A=Not applicable; Q12H=every 12 hours

The classification of Investigational Medicinal Product (IMP) and Non-Investigational Medicinal Product (NIMP) in this table is based on guidance issued by the European Commission and applies to countries in the European Economic Area (EEA). Country differences with respect to the definition/classification of IMP/NIMP may exist. In these circumstances, local legislation is followed.

a Capsules will be administered by mouth. For participants unable to swallow study medication capsules during the treatment period, dosing of capsule contents via alternative routes (eg, nasogastric tube, orogastric tube, etc.) will be allowed.

b MK-4482 dose for Part 2 will be determined based on assessment of results of Part 1 and the totality of data available across the MK-4482 clinical program prior to initiating Part 2.

All supplies indicated in **Table 1** will be provided per the "Sourcing" column depending upon local country operational requirements. If local sourcing, every attempt should be made to source these supplies from a single lot/batch number where possible (eg, not applicable in the case where multiple lots or batches may be required due to the length of the study, etc.).

Refer to Section 8.1.8 for details regarding administration of the study intervention.

## **6.2 Preparation/Handling/Storage/Accountability**

### **6.2.1 Dose Preparation**

There are no specific calculations or evaluations required to be performed in order to administer the proper dose to each participant. The rationale for selection of doses to be used in this study is provided in Section 4.3.

For participants unable to swallow study medication capsules during the treatment period, dosing of capsule contents via alternative routes (eg, nasogastric tube, orogastric tube, etc.) will be allowed. Preparation details will be provided in the pharmacy manual.

### **6.2.2 Handling, Storage, and Accountability**

The investigator or designee must confirm appropriate temperature conditions have been maintained during transit for all study intervention received, and any discrepancies are reported and resolved before use of the study intervention.

Only participants enrolled in the study may receive study intervention, and only authorized site staff may supply or administer study intervention. All study interventions must be stored in a secure, environmentally controlled, and monitored (manual or automated) area in accordance with the labeled storage conditions with access limited to the investigator and authorized site staff.

The investigator, institution, or the head of the medical institution (where applicable) is responsible for study intervention accountability, reconciliation, and record maintenance (ie, receipt, reconciliation, and final disposition records).

For all study sites, the local country Sponsor personnel or designee will provide appropriate documentation that must be completed for drug accountability and return, or local discard and destruction if appropriate. Where local discard and destruction is appropriate, the investigator is responsible for ensuring that a local discard/destruction procedure is documented.

The study site is responsible for recording the lot number, manufacturer, and expiry date for any locally purchased product (if applicable) as per local guidelines unless otherwise instructed by the Sponsor.

The investigator shall take responsibility for and shall take all steps to maintain appropriate records and ensure appropriate supply, storage, handling, distribution, and usage of study interventions in accordance with the protocol and any applicable laws and regulations.

### **6.3 Measures to Minimize Bias: Randomization and Blinding**

#### **6.3.1 Intervention Assignment**

Intervention randomization will occur centrally using an IRT system. In Part 1, there are 4 study intervention arms and participants will be assigned randomly in a 1:1:1:1 ratio to MK 4482 200 mg, 400 mg, 800 mg, or placebo. In Part 2, there are 2 study intervention arms and participants will be assigned randomly in a 1:1 ratio to MK-4482 (at selected dose) or placebo.

#### **6.3.2 Stratification**

Intervention randomization will be stratified according to the following factors:

1. Time from symptom onset prior to the day of randomization ( $\leq 5$  days,  $>5$  days)
2. Age ( $\leq 60$  years,  $>60$  years)
3. Remdesivir use for treatment of the index diagnosis of COVID-19 prior to or at the time of randomization (yes, no)

Based on the viral kinetics of SARS-CoV-2 and the mechanism of action of MK-4482, treatment with antiviral therapy is likely to have a greater benefit with early treatment ( $\leq 5$  days) rather than late treatment ( $>5$  days). Older age is also associated with more severe outcomes, and the WHO notes that people older than 60 years are at higher risk for severe illness due to COVID-19. Finally, remdesivir has been demonstrated to shorten the time to recovery in hospitalized patients with COVID-19 and may be used concurrently in this study. The selection of these criteria as stratification factors will help ensure that the treatment groups will be well balanced within each stratum and the study results will not be confounded by factors suspected to have a potential impact on a participant's response to study intervention.

Of note, enrollment of participants with severe COVID-19 (Appendix 9) will be limited to 50% of the total planned sample size in both Parts 1 and 2.

#### **6.3.3 Blinding**

A double-blinding technique with in-house blinding will be used. MK-4482 (all dose levels) and placebo will be packaged identically so the blind is maintained. The participant, the investigator, and Sponsor personnel or delegate(s) who are involved in the study intervention administration or clinical evaluation of the participants are unaware of the intervention assignments.

Blinding of capsule contents for use via alternate routes (nasogastric tube, orogastric tube, etc.) will be performed by the unblinded site pharmacist or designee. Preparation details will be provided in the pharmacy manual.

To allow timely completion of dose/exposure-response analyses, select Sponsor internal or external personnel will be unblinded while Part 1 of the study is ongoing. No personnel directly associated with study conduct will be unblinded (before Part 1 database lock). Before granting select personnel access to unblinded Part 1 data, an official memo detailing the unblinding procedures and listing the personnel who will have access (before database lock) to the unblinded data will be generated per Sponsor SOP. Once all Part 1 participants have completed Day 29 (ie, achieved a final status for Day 29 endpoints), the Sponsor will initiate database lock/unblinding procedures for this part of the study. Internal blinding will be maintained for Part 2 participants until all Part 2 participants have completed Day 29 (ie, achieved a final status for Day 29 endpoints) except as documented in Section 9.7 – Interim Analyses.

#### **6.4 Study Intervention Compliance**

When participants are dosed at the site, they will receive study intervention directly from the investigator or designee, under medical supervision. If local infection control restrictions do not allow for medical supervision, the study intervention must be administered by appropriately qualified institution (eg, hospital, clinic) staff. The date and time of each dose administered in the clinic will be recorded in the source documents and recorded in the CRF. The dose of study intervention and study participant ID will be confirmed at the time of dosing by a member of the study site staff other than the person administering the study intervention. If local infection control restrictions do not allow for a confirmation at the time of dosing by a separate study site staff member, the study intervention administration source documentation must be contemporaneously reviewed by a member of the study site staff other than the person administering study intervention.

For participants who are discharged prior to receiving all 10 doses of study intervention, a Study Medication Diary will be provided for documentation of doses and assessment of compliance (Section 8.1.14).

A record of the number of capsules dispensed to and taken by each participant must be maintained and reconciled with study intervention and compliance records. Intervention start and stop dates, including dates for intervention delays and/or dose reductions will also be recorded in the CRF. Deviation(s) from the prescribed dosage regimen should be recorded in the CRF.

#### **6.5 Concomitant Therapy**

Medications or vaccinations specifically prohibited in the exclusion criteria are not allowed during time periods specified by this protocol for those medications or vaccinations. If there is a clinical indication for any medications or vaccinations specifically prohibited, discontinuation from study intervention may be required. The investigator should discuss any questions regarding this with the Sponsor Clinical Director. The final decision on any

supportive therapy or vaccination rests with the investigator and/or the participant's primary physician. However, the decision to continue the participant on study intervention requires the mutual agreement of the investigator, the Sponsor, and the participant.

Any medication or vaccine (including over-the-counter or prescription medicines, vitamins, and/or herbal supplements or other specific categories of interest) that the participant is receiving at the time of enrollment or receives during the study must be recorded per data entry guidelines.

Prior and concomitant therapies listed as prohibited in [Table 2](#) are not permitted for the specific time frames listed. [Table 2](#) is not comprehensive, and the investigator should use his/her medical judgment when assessing whether a participant's prior and concomitant therapy(ies) are prohibited. The Sponsor Clinical Director or designee should be contacted if there are any questions about a therapy not listed or regarding potential DDIs with a specific treatment that the participant may plan to receive.

Table 2 Prohibited and Allowed Therapies

COVID-19 Vaccines	

SARS-CoV-2 vaccines are prohibited any time prior to randomization and through Day 29.

COVID-19 Therapeutics	

Sponsor-designated standard of care for treatment for COVID-19 is permitted (eg, remdesivir, corticosteroids, etc.) but may require additional safety monitoring as determined by the treating clinician.

If guidelines for local standard of care conflict with Sponsor-designated standard of care, site should consult with Sponsor.

Supportive therapies (including but not limited to anti-pyretic and anti-inflammatory agents) to manage COVID-19 signs/symptoms are allowed.

Unless designated by the Sponsor as acceptable standard of care for COVID-19, concomitant use of other therapies intended as specific treatment for COVID-19 are prohibited from randomization through Day 29.

Non-COVID-19 Investigational agents	All non-COVID-19 investigational agents including devices are prohibited within 30 days prior to randomization and through Day 29.

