### **8.1.5 Prior and Concomitant Medications Review**

#### **8.1.5.1 Prior Medications**

The investigator or qualified designee will review prior medication use and record prior medications taken by the participant within 30 days before first dose of study intervention. All prior therapeutics/vaccines for COVID-19, regardless of timing, must be recorded.

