Blinding to treatment assignment will be maintained at all investigational sites. The results of interim analyses will not be shared with the investigators prior to the completion of the study. Participant-level unblinding will be restricted to an internal (or external, as appropriate) unblinded cross-functional team performing the interim analyses and dose recommendation, who will have no other responsibilities associated with the study.

There will be 3 interim analyses during the study as shown in [Table 7](#).

Table 7 Description of Interim Analyses

Interim Analysis	Timing	P001 Primary Data for Analysis	Committee Action
IA1 – Part 1 Dose Evaluation	Targeted to occur during Phase 2 after ~300 participants complete EOT combined in MK-4482-001 and MK-4482-002 a .	PK, available virologic, safety & efficacy data through EOT	eDMC recommendation for discontinuation of the study or protocol modifications Sponsor siDMC review of interim safety data and review of preliminary virology data Review by the unblinded team to inform dose selection models and analyses
IA2 - Part 1 b Dose Selection	Targeted to occur at the completion of Phase 2 after ~300 participants complete Day 29 (includes participants from IA1).	PK, safety & efficacy data through Day 29 and available virologic data	eDMC recommendation for discontinuation of the study or protocol modifications Sponsor siDMC approval of proposed MK-4482 dose for Part 2.
IA3 – Part 2 Futility/Early Efficacy	Targeted to occur during Phase 3 after ~343 of an expected 685 sustained recovery events, expected to be at approximately 50% of the full planned enrollment in the selected MK-4482 group and the placebo group in Part 2.	Safety & efficacy data through Day 29	Futility and early efficacy to be assessed by eDMC per eDMC Charter and guided by statistical criteria

eDMC=external Data Monitoring Committee; EOT=End of Treatment; IA=Interim Analysis; PK=pharmacokinetics; siDMC=standing internal Data Monitoring Committee.

a P002 is a companion MK-4482 dose-ranging study in non-hospitalized adults with COVID-19

b IA2 represents the analysis of the full Part 1 cohort of participants through Day 29.

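### No written criterion excludes a participant who has just completed or stopped an experimental COVID-19 therapy, including MK-4482 from the companion outpatient study

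*Combined protocol and SAP*

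**What the plan says.** Table 2 in Section 6.5 sets three time windows:

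- Vaccines: "SARS-CoV-2 vaccines are prohibited any time prior to randomization and through Day 29".
- Investigational agents not aimed at COVID-19: "All non-COVID-19 investigational agents including devices are prohibited within 30 days prior to randomization and through Day 29".
- COVID-19 therapeutics: the sponsor's designated standard of care is allowed; otherwise "concomitant use of other therapies intended as specific treatment for COVID-19 are prohibited from randomization through Day 29".

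Two exclusion criteria in Section 5.2 bear on the point. Criterion 10 excludes a person who "Is taking or is anticipated to require any prohibited therapies as outlined in Section 6.5". Criterion 11 excludes a person who "Is unwilling to abstain from participating in another interventional clinical trial through Day 29 with an investigational compound or device", and it names COVID-19 therapeutics among the compounds meant.

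Section 8.1.5.1 collects the history: "All prior therapeutics/vaccines for COVID-19, regardless of timing, must be recorded". Section 9.7, Table 7, footnote a identifies MK-4482-002: "P002 is a companion MK-4482 dose-ranging study in non-hospitalized adults with COVID-19". Section 5.1 admits hospitalized patients whose symptoms began no more than 10 days before randomization.

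**The concern.** Of the prohibited classes in Table 2, the one most able to move the endpoints, COVID-19 therapy outside designated standard of care, has no look-back. A completed course, or a single infusion given days before entry, meets no exclusion.

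MK-4482-002 makes the route concrete. It enrols non-hospitalized adults with COVID-19 and runs alongside Part 1. A participant dosed there who worsens and is admitted within 10 days of onset can meet inclusion criteria 1 to 4 here. If that person is willing to leave the other study, nothing written keeps them out, and they could be randomized to placebo shortly after taking active drug.

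Two results are at stake. One is the H1 contrast in Part 2, which weakens if some participants in both arms already carry the effect under test. The other is the Part 1 viral RNA comparison at Day 3 and EOT, which Section 9.6.1 calls important for dose selection and which has about 75 participants per arm. Section 6.3.2 stratifies only for remdesivir among prior therapies, and Section 9.10 lists only remdesivir and corticosteroid subgroups. Because such entry breaks no written rule, it need not count as a deviation that removes the participant from the Per-Protocol population (Section 9.5.1).

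**Working it through.** **1. Does any written rule look back?**

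| Rule | Period covered | Catches a COVID-19 agent stopped before randomization? |
|---|---|---|
| Table 2, vaccines | Any time before randomization to Day 29 | No, vaccines only |
| Table 2, non-COVID-19 investigational agents | 30 days before randomization to Day 29 | No, its label excludes COVID-19 agents |
| Table 2, COVID-19 therapeutics | Randomization to Day 29 | No |
| Exclusion 10 | Current or expected use | No; catches use continuing at entry |
| Exclusion 11 | Willingness to abstain through Day 29 | No; looks forward |

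Exclusion 10 has no window of its own. It relies on Section 6.5, which applies each prohibition for the time frame shown in Table 2. No criterion in Sections 5.1 or 5.2 names earlier MK-4482.

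**2. Reproduce the design power (Sections 9.7 and 9.9.1).** Inputs: rate ratio 1.3, 343 interim and 685 final events, 1:1 allocation, one-sided alpha 0.025, Gamma spending with γ = −1, futility bound at rate ratio 1.071.

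- Interim alpha = 0.025 × (1 − e^0.5)/(1 − e) = 0.0094, so z1 = 2.348. Rate ratio bound = exp(2 × 2.348/√343) = 1.289. The plan states 0.009 and 1.289.
- Final bound, spending the remaining alpha with correlation √(343/685): z2 = 2.066, p = 0.0194, rate ratio exp(2 × 2.066/√685) = 1.171. The plan states 0.019 and about 1.17.
- Futility z = ln(1.071) × √343/2 = 0.635. Crossing probability is 73.7% under H0 and 3.6% under H1. The plan states 74% and 3.6%.
- Mean z under H1 = ln(1.3) × √343/2 = 2.430 at the interim and ln(1.3) × √685/2 = 3.433 at the end. Bivariate normal integration, with a futility crossing counted as a stop, gives power 90.4%. The plan states 90%.

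**3. Dilution.** The documents give no share, so c is an assumption. Suppose a share c of each arm is already effectively treated and gains nothing more. To a good approximation the log rate ratio becomes (1 − c) × ln(1.3). Boundaries and event counts are unchanged.

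| Assumed c | Rate ratio | Power |
|---|---|---|
| 0% | 1.300 | 90.4% |
| 1% | 1.297 | 89.8% |
| 2% | 1.293 | 89.3% |
| 5% | 1.283 | 87.3% |
| 10% | 1.266 | 83.6% |

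**4. Part 1 noise.** With 75 per arm, the SD of the chance difference in the pre-treated share between two arms is √(2c(1 − c)/75): 1.6 percentage points at 1%, 2.3 at 2%, 3.6 at 5% and 4.9 at 10%.

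**The case against.** Several safeguards exist. Section 6.5 says Table 2 is not exhaustive, applies investigator judgment expressly to prior therapy, and sends questions about unlisted therapies to the Sponsor Clinical Director. Exclusion 9 lets the investigator exclude for a condition that could confound the assessments. Section 9.6.1 uses change from baseline in viral RNA, explores subgroups by baseline level, and plans analyses without participants who have low baseline levels. Section 9.6.3 tabulates prior therapies by arm. These stand as partial protection, but the discretionary ones set no window and may be applied differently across sites, and a low baseline value does not identify everyone pre-treated.

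The size is also unknown. How often someone leaves MK-4482-002 for this study depends on that study's follow-up and withdrawal rules, which are not in these documents; nor is the list of designated standard-of-care therapies. Whether remaining in follow-up there counts as participating under exclusion 11 is not stated. All of this stands.

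A reader might infer four stronger things that the documents do not support:

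- That the non-COVID-19 row is the sole look-back in Table 2. The vaccine row has one too.
- That people still taking a prohibited COVID-19 agent can enter. Exclusion 10 with Table 2 catches them.
- That the comparison is biased or type I error inflated. Earlier treatment is fixed before randomization, so it is balanced in expectation.
- That someone in both studies would count twice in a pooled IA1 analysis. The combined count of about 300 sets the timing of IA1, the data column of Table 7 is headed as P001 data, and no pooled participant-level test is described. Dose selection comes at IA2.

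**Conclusion.** The gap is real and lies in the written criteria: a completed or stopped experimental COVID-19 therapy, or earlier MK-4482, is not excluded, and only judgment stands in the way. The consequence is dilution of the Part 2 contrast and added noise in the Part 1 viral RNA dose-response.

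Its size depends on a share the documents do not give. At 1% to 2%, the power loss is about one percentage point or less. At 5% it is about 3 points (90.4% to 87.3%) and at 10% about 7 (90.4% to 83.6%). These figures assume an equal share in each arm, no further benefit in those participants, and unchanged event counts. At the low end, the stronger reason to act is that the placebo arm and the dose groups should mean what their labels say. This is a worthwhile, inexpensive correction; it does not undermine the design.

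**What to change.** 1. Reconcile the COVID-19 therapeutics row of Table 2 with exclusions 10 and 11 so that investigational COVID-19 therapy received before randomization is explicitly covered. The length of any window is for the sponsor to set. State whether continued follow-up in another trial counts as participation under exclusion 11.
2. Add an exclusion for earlier receipt of study intervention in any MK-4482 study, including MK-4482-002.
3. For anyone already enrolled, flag such participants from the prior-therapy data required by Section 8.1.5.1. In Section 9.6.1, and in the separate dose-response analysis plan, pre-specify a sensitivity analysis of the primary endpoint and of the Part 1 viral RNA dose-response without them. As the flag rests on pre-randomization data, it can be set before unblinding.

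The cost is an amendment to one table row and the exclusion criteria, and a small loss of eligible patients. The analysis flag needs no new data, and the sample size and boundaries do not change.
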